7.5. Adjustments for Multiple Comparisons

No adjustments will be made for multiple comparisons.

7.6. Demographic and Other Baseline Characteristics

The total number of males and females who participate in the study will be reported. The average age and standard deviation of the study subjects will be reported. The number and percentage of subjects with a medical history of sinus node dysfunction, AV junctional arrhythmias and blocks, and heart failure will be reported. The number and percentage of subjects with an AV node ablation in their medical history will be reported.

7.7. Treatment Characteristics

Using device data from study save-to-disk files, the device longevity estimate from the last available file for each subject will be used to calculate a survival function estimate for the device battery. Programmed outputs at implant and changes over time shall also be summarized. Tools used during the implant procedure will be summarized with counts and percentages including the type of delivery catheter. Further analysis of implant tools is included in Ancillary Objective #1. Other implant characteristics are included in the analysis of Ancillary Objective #2.

7.8. Interim Analyses

No interim analysis will be conducted.

7.9. Evaluation of Objectives

7.9.1. Primary Objective

The primary objective is to assess the implant success proportion of the Medtronic SelectSecure™ MRI SureScan™ Model 3830 pacing lead at the bundle of His for His Bundle Pacing.

Analysis Dataset:

Analysis set #1 per section 7.1.3.

Analysis Method:

The observed implant success proportion will be calculated as follows:

$$\text{Implant Success Proportion} = \frac{\text{\# Subjects with implant success}}{\text{\# Subjects with implant attempt}}$$

A 95% confidence interval for the implant success proportion will be constructed using the Wilson method. The analysis will also provide a table summarizing implant success, similar to the following:

	Number (Percentage)
Successful	N (xx%)
Unsuccessful	N (xx%)
Reason 1	N (xx%)
Reason 2	N (xx%)

The observed implant success proportion will be calculated using SAS code similar to the following:

```
proc freq data=analysisset1;
  table impsuccess / alpha=0.05 binomial(level='Yes' wilson);
  output out=impc1 binomial;
run;
```

Endpoint Definition:

Implant success will be defined as the presence of a H wave on the implanted lead EGM and a HB pacing capture threshold equal to or less than 2.5V at 1.0ms.

Implant success proportion is defined as the proportion of all subjects who undergo an implant attempt that is successful.

Additional Analysis:

Implant success may also be characterized in subgroups of subjects with different classifications of AV block or sinus node dysfunction. Characterizations shall only be performed if there is sufficient data (e.g. 10 patients) within each subgroup.

7.9.2. Secondary Objective #1

This secondary objective is to estimate the correlation between the lead position and selective vs. non-selective HBP occurrence at implant.

Analysis Dataset:

Analysis set #2 per section 7.1.3.

Analysis Method:

The relationship between lead position (anterior septum, mid septum, posterior septum) and HBP selectivity (selective vs. non-selective) will be assessed using a logistic regression. Additionally, HV intervals will be compared between the three groups of lead positions using linear regression. The logistic regression will be performed in SAS using code similar to:

```
proc genmod data=analysisset2;
  class leadloc;
  model nsHBP = leadloc / dist = bin link=logit;
```

```
run;
```

and the linear regression will be performed in SAS with code similar to:

```
proc glm data=analysisset2;
  class leadloc;
  model HVint = leadloc;
run;
```

Endpoint Definition:

The lead position is identified as anterior septum, mid septum or posterior septum. Location is determined by the implanting physician during implant and verified by Medtronic through evaluation of cardiac CT scan images. The location determined from CT scan will be used in the analysis.

The HBP at implant is classified as either selective or non-selective by the implanting physician based on the definitions specified in section 4.1, Table 1 of the study CIP.

Additional Analysis:

None

7.9.3. Secondary Objective #2

This secondary objective is to assess changes in lead electrical measurements over time (HB PCT, R waves and impedance).

Analysis Dataset:

Analysis set #2 per section 7.1.3.

Analysis Method:

The lead electrical measurements from each visit will be summarized using descriptive statistics (number with measure available, mean, median, standard deviation, minimum, maximum) and graphical displays. Longitudinal analysis will be conducted to estimate differences in electrical measurements from implant to subsequent follow-up visits. The analysis will be performed in SAS using code similar to:

```
proc mixed data=analysisset2;
  class time;
  model pct = time;
  random int / subj=ptid corr=exch;
run;
```

Endpoint Definition:

The lead electrical measurements that will be evaluated include HB pacing capture threshold (PCT) (in Volts) at 0.5ms, impedance (in Ohms), and R-wave amplitude (in mV) measured at the final lead location during the implant procedure, and then at the 3-month, 6-month, and 12-month follow-up visits.

Additional Analysis:

A similar analysis will be performed using the HB PCT at a pulse width of 1.0ms, instead of a pulse width of 0.5ms.

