## 13.2.2.3. Analysis Methods

The lead electrical measurements from each visit will be summarized using descriptive statistics (mean, median, standard deviation, minimum, maximum, etc.) and graphical displays. Longitudinal analysis will be conducted to estimate differences in electrical measurements from implant to subsequent follow-up visits.

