7.1.3. Analysis Sets

There will be two analysis sets used in this study:

Analysis Set #1:

This analysis set will be used for the primary objective (implant success), secondary objective #5 (adverse events), and ancillary objectives #1 and #2. Study subjects will be included in this analysis set if an implant is attempted.

A STROBE flow diagram per section 7.1.1 will outline the specific exclusions.

Analysis Set #2:

This analysis set will be used for secondary objectives #1-#4 and ancillary objective #3. Study subjects will be included in this analysis set if they have a successful implant.

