7.2.3. Secondary Objective #2

This secondary objective is to assess changes in lead electrical measurements over time (HB PCT, R waves and impedance).

The lead electrical measurements from each visit will be summarized using descriptive statistics (mean, median, standard deviation, minimum, maximum, etc.) and graphical displays. Longitudinal analysis will

be conducted to estimate differences in electrical measurements from implant to subsequent follow-up visits.

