7.9.4. Secondary Objective #3

This secondary objective is to assess changes in QRS duration over time.

Analysis Dataset:

Analysis set #2 per section 7.1.3.

Analysis Method:

The QRS durations from each visit will be summarized using descriptive statistics (number with measure available, mean, median, standard deviation, minimum, maximum) and graphical displays. Longitudinal analysis will be conducted to estimate differences in QRS duration from implant to subsequent follow-up visits. The analysis will be performed in SAS using code similar to:

```
proc mixed data=analysisset2;
  class time;
  model inqrs = time;
  random int / subj=ptid corr=exch;
run;
```

Endpoint Definition:

Intrinsic QRS duration will be measured prior to the implant procedure, and then at the 3-month, 6-month, and 12-month follow-up visits.

Additional Analysis:

A similar analysis will be performed using the paced QRS duration instead of intrinsic QRS duration.

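### The repeated-measures model for Secondary Objectives 2 and 3 assumes compound symmetry with no safeguard, so intervals for change from implant could be too narrow; an unstructured covariance avoids this at little cost

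*SAP*

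**What the plan says.** The target is the same in both documents. Protocol 13.2.2.3 states: "Longitudinal analysis will be conducted to estimate differences in electrical measurements from implant to subsequent follow-up visits". SAP 7.2.3 repeats it. For Objective 2 the readings are threshold at 0.5 ms, impedance and R wave, "measured at the final lead location during the implant procedure, and then at the 3-month, 6-month, and 12-month follow-up visits". For Objective 3: "Intrinsic QRS duration will be measured prior to the implant procedure, and then at the 3-month, 6-month, and 12-month follow-up visits". Each model therefore has four time points. SAP 7.9.3 adds a parallel analysis of the 1.0 ms threshold, and SAP 7.9.4 adds one of paced QRS.

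The prose never names a model or a covariance structure. Those appear only in the SAS code, which SAP 7.9.3 introduces with "The analysis will be performed in SAS using code similar to". The code has visit as the only fixed effect and ends with "random int / subj=ptid corr=exch". SAP 7.9.4 uses the same RANDOM line with "model inqrs = time". There is no REPEATED statement, robust variance option, alternative structure or fallback. The code contains no LSMEANS, ESTIMATE or SOLUTION/CL request, and the text names no interval or confidence level for the change.

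The analysis set is Set #2 (SAP 7.1.3): "Study subjects will be included in this analysis set if they have a successful implant". SAP 7.4 rules out imputation and drops subjects with missing data.

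**The concern.** A random intercept plus one residual variance is compound symmetry. It treats the implant visit as exchangeable with the 3-, 6- and 12-month visits, although implant is the reference for every contrast of interest and differs from the others in two ways. It is an acute reading, and Protocol 9.7 has it taken through the analyzer as well as the device, whereas Protocol 9.8.3 and 9.8.4 use the implanted generator and programmer. It is plausible that an implant reading predicts a chronic reading less well than one chronic reading predicts another. The protocol itself treats the link between implant threshold and 12-month threshold as an open question (Secondary Objective 4).

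If so, the model averages the large variance of implant-to-chronic differences with the small variance of chronic-to-chronic differences. Change from implant then gets too small a standard error, and change between chronic visits gets too large a one. At stake is the error bar on the quantity these objectives set out to estimate.

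**Working it through.** **Plan's own figure.** Neither document gives a precision figure, SD or correlation for Objectives 2 or 3. The SAP's only precision figures are Wilson widths for implant success. The 0.17 at 50 attempts and 0.90 success reproduces (0.1701) but has no bearing here.

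**Inputs from the documents.** Four visits. Set #2 size at 0.90 success: 0.9 × 50 = 45 under the SAP, and 0.9 × 62 = 55.8, about 56, under the protocol.

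**Assumptions.** Visit SDs and correlations. Write r₀ for the correlation between implant and any chronic visit, and r_c for that between two chronic visits. SDs are in units of the implant SD.

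**Formulas (complete data).**
- True variance of the 12-month change: (s₀² + s₁₂² − 2·cov)/n.
- Variance the random-intercept model uses for every contrast: the mean of Var(difference) over the six visit pairs, divided by n, with 3(n−1) degrees of freedom.
- Coverage ≈ P(|Z| < t × SE ratio), where SE ratio = model SE / true SE.
- For n = 45: 3 × 44 = 132 df, t = 1.978.

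**Equal SDs, unequal correlations.** Three of the six pairs involve implant, with Var = 2(1−r₀). The other three have Var = 2(1−r_c).

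| r₀ / r_c | Implant–chronic Var | Chronic–chronic Var | Mean (model) | SE ratio | Coverage, 12-month change |
|---|---|---|---|---|---|
| 0.8 / 0.8 | 0.4 | 0.4 | 0.4 | 1.000 | 95.2% |
| 0.6 / 0.8 | 0.8 | 0.4 | 0.6 | √(0.6/0.8) = 0.866 | 91.3% |
| 0.4 / 0.8 | 1.2 | 0.4 | 0.8 | √(0.8/1.2) = 0.816 | 89.4% |
| 0.3 / 0.9 | 1.4 | 0.2 | 0.8 | √(0.8/1.4) = 0.756 | 86.5% |

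With n = 56 the figures change by no more than 0.1 percentage point. In the last three rows the 3- to 12-month contrast errs the other way: SE ratios 1.225, 1.414 and 2.0, coverage 98.5% to 100%. As chronic visits become identical, the SE ratio tends to √0.5 = 0.707 and coverage to about 83% (1.96 × 0.707 = 1.386).

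**Unequal SDs, equal correlations.** Chronic SD 1.5 times implant, r = 0.5: true 1 + 2.25 − 1.5 = 1.75; chronic pairs 2 × 2.25 × 0.5 = 2.25; mean 2.0; SE ratio √(2.0/1.75) = 1.069; coverage 96.6%. Chronic SD twice implant, r = 0.8: true 1.8, chronic pairs 1.6, mean 1.7; SE ratio 0.972; coverage 94.5%. Over SD ratios 1.25 to 2 and r of 0.5 or 0.8, coverage runs from 94.5% to 96.7%.

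**Unstructured covariance.** With complete data it gives the paired interval on n−1 df. Simulated coverage (6,000 runs per scenario) for the 12-month change was 94.3% to 95.7% in every scenario, with n = 45 or 56, SD ratios 1 to 2, and equal or unequal correlations.

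**Heterogeneous compound symmetry.** This frees the four variances but keeps one correlation. Its large-sample best fit to the three unequal-correlation rows gives SE ratios 0.884, 0.848 and 0.807, so (with t = 1.98) coverage of about 92%, 91% and 89%. Most of the shortfall remains.

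**The case against.** The strongest reply is that nothing in the documents shows compound symmetry to be false. No SD or correlation is given for any outcome, and if the assumption holds the intervals are right (95.2% above). The code is offered as an illustration, the objectives are descriptive with no performance requirement, and no interval is named. With complete data the estimated changes are the same under either covariance. All of this stands and limits the weight of the point. It does not remove it: the code is the only place where a model is stated, `exch` signals that equal correlation is intended, and a descriptive estimate of change still needs a sound error bar.

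A reader might infer more in three places, and the documents do not support it.

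- **That the 2.5 V success limit spoils the intervals by truncating implant spread.** Unequal variance alone is nearly harmless, as shown. The limit also applies only to the threshold at 1.0 ms, while the main Objective 2 outcome is the threshold at 0.5 ms. It has no bearing on R wave, impedance or QRS.
- **That the acute-reading argument covers every outcome equally.** Intrinsic QRS is first measured before the procedure, so lead-based reasoning does not reach it. The equipment contrast is also partial, since the device is used at implant too.
- **That missed visits make matters worse.** SAP 7.4 excludes subjects with missing data, and no size for such an effect can be derived from the documents.

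**Conclusion.** The point holds in conditional form. SAP 7.9.3 and 7.9.4 commit, as far as they commit to anything, to compound symmetry without a safeguard. Under assumed equal SDs and implant–chronic against chronic–chronic correlations of 0.6/0.8, 0.4/0.8 or 0.3/0.9, a nominal 95% interval for the 12-month change covers about 91%, 89% or 86%. An unstructured covariance holds about 95% in the same settings and loses almost nothing when compound symmetry is true. The driver is the gap between the two correlations, not unequal variance.

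It would be tempting to conclude that the planned intervals are wrong. That is not established: it depends on correlations the documents do not give. This is a worthwhile, low-cost improvement to a descriptive secondary analysis.

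**What to change.** In SAP 7.9.3 and 7.9.4:

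1. Replace the RANDOM line with `repeated time / subject=ptid type=un;` and add `ddfm=kr` to the MODEL statement. The line needs correcting in any case: `corr=exch` is working-correlation syntax from the GENMOD REPEATED statement, not an option of the PROC MIXED RANDOM statement.
2. Request each visit-minus-implant difference (visit minus pre-implant for intrinsic QRS) with its 95% confidence interval, and say so in the text. Apply this to threshold at 0.5 and 1.0 ms, R wave, impedance, and intrinsic and paced QRS.
3. Name a fallback if the unstructured model does not converge: robust (EMPIRICAL) standard errors or paired-difference intervals. Heterogeneous compound symmetry should not be the fallback, because it keeps the single common correlation.

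The cost is a few lines of code and text. Four visits need ten covariance parameters in place of two, which about 45 to 56 subjects can support, and there are somewhat fewer degrees of freedom. When compound symmetry is true with equal SDs and r = 0.8, the 95% half-width for n = 45 rises only from 0.186 to 0.190 implant SDs. The SAP was written from CIP Version 2.0 and the protocol is now Version 4.0, so this can go into the same revision that aligns them.

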7.9.4. Secondary Objective #3

This secondary objective is to assess changes in QRS duration over time.

Analysis Dataset:

Analysis set #2 per section 7.1.3.

Analysis Method:

The QRS durations from each visit will be summarized using descriptive statistics (number with measure available, mean, median, standard deviation, minimum, maximum) and graphical displays. Longitudinal analysis will be conducted to estimate differences in QRS duration from implant to subsequent follow-up visits. The analysis will be performed in SAS using code similar to:

```
proc mixed data=analysisset2;
  class time;
  model inqrs = time;
  random int / subj=ptid corr=exch;
run;
```

Endpoint Definition:

Intrinsic QRS duration will be measured prior to the implant procedure, and then at the 3-month, 6-month, and 12-month follow-up visits.

Additional Analysis:

A similar analysis will be performed using the paced QRS duration instead of intrinsic QRS duration.

7.9.5. Secondary Objective #4

This secondary objective is to estimate the correlation between implant characteristics and long-term lead electrical performance at 12 months post-implant.

Analysis Dataset:

Analysis set #2 per section 7.1.3.

Analysis Method:

A multivariable regression analysis will be conducted to assess if there is any correlation between implant characteristics, including lead location, HB PCT, and paced QRS duration at implant, and the 12-month HB PCT. The analysis will be performed in SAS using code similar to:

```
proc glm data=analysisset2;
  class leadloc;
  model pct12 = pct0 leadloc pacedqrs0;
run;
```

Endpoint Definition:

Long-term lead electrical performance is identified as the HB PCT with a pulse width of 0.5ms at 12 months post-implant. Implant characteristics to be evaluated here include lead location, HB PCT with a pulse width of 0.5ms at implant, and paced QRS duration at implant. The lead location is determined by the implanting physician during implant and verified by Medtronic through evaluation of cardiac CT scan images. The location determined from CT scan will be used in the analysis.

Additional Analysis:

A similar analysis will be performed using the implant and 12 month HB PCT at a pulse width of 1.0ms, instead of a pulse width of 0.5ms. In addition, the number of subjects that have an increase of 1.0V in the HB PCT will be characterized, and further this characterization will be performed on the subgroups of subjects with either AV block or sinus node dysfunction.

The association between lead slack, anatomical features and HB PCT may also be analyzed. Lead slack = Arclength/Euclidean distance as determined from the CT scan. Anatomical features include right atrial size and location of right atrial dilation.

7.9.6. Secondary Objective #5

This secondary objective is to characterize the occurrence of any complications related to the procedure or the lead for His bundle pacing up to 12 months post-implant.

Analysis Dataset:

Analysis set #1 per section 7.1.3.

Analysis Method:

The types of complications related to the procedure or the lead for His bundle pacing will be summarized using frequencies and percentages. The probability of a subject being free of a complication related to the procedure or the lead for His bundle pacing through 12 months post-implant will be estimated using the Kaplan-Meier method.

The Kaplan-Meier analysis will be performed in SAS using code similar to:

```
proc lifetest data=analysisset1 conftype=loglog timelist=12;
  time monthsEvent*event(0);
run;
```

In addition, the relationship between implant characteristics, including lead position, HB PCT at implant, and QRS duration at implant, and the occurrence of complications related to the procedure or the lead for His bundle pacing will be assessed using a Cox proportional hazard regression model. The Cox proportional hazards analysis will be performed in SAS using code similar to:

```
proc phreg data=analysisset;
  class leadloc;
  model monthsEvent*event(0) = leadloc pct0 pacedqrs0;
run;
```

Endpoint Definition:

Procedure and the lead for His bundle pacing related complications will be reported via the Adverse Event eCRF. Examples include but are not limited to: lead dislodgement, exit block, loss of capture, or high threshold causing action.

Additional Analysis:

All adverse events collected in the study will be characterized. A table with MedDRA Preferred terms will be generated, which will report for each MedDRA Preferred term, the number of adverse events, the number of subjects with event, and these numbers also restricted to complications. This table will be similar to:

Table 2. MedDRA terms

MedDRA Preferred Term	Adverse events		Complications	
	lead related	procedure related	lead related	procedure related
Exit block	1 (1)	0 (0)	0 (0)	0 (0)
High threshold	1 (1)	0 (0)	1 (1)	0 (0)

MedDRA Preferred Term	Adverse events		Complications	
	lead related	procedure related	lead related	procedure related
Lead dislodgment	2 (2)	0 (0)	1 (1)	0 (0)
Loss of capture	4 (3)	1 (1)	2 (2)	0 (0)

A listing of all adverse events will be generated, with subject identifier, time of event relative to the implant procedure, event description, classification, outcome and MedDRA Preferred term.

Adverse events in subjects with an unsuccessful implant will be reported separately. Additionally, events in subjects that had no implant attempt will be reported separately. Complications will also be characterized for the subgroups of subjects with either AV block or sinus node dysfunction.

In addition, the major complication rate will be estimated using the Kaplan-Meier method where a major complication is defined as a complication that leads to:

- Death
- Permanent loss of device function due to mechanical or electrical dysfunction of the device (e.g. loss of capture, lead dislodgement)
- Hospitalization
- Prolonged Hospitalization by at least 48 hours
- System revision (reposition, replacement, explant)

These components of a major complication will be determined from the MUO Adverse Event CRF.

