# Imaging Study of Lead Implant for His Bundle Pacing Clinical Investigation Plan

056-F275

Version 4.0

Page 11 of 57

Medtronic

	

• Estimate the correlation between lead position and selective vs. non-selective His bundle pacing occurrence at implant

• Assess changes in lead electrical measurements over time

• Assess changes in QRS duration over time

• Estimate the correlation between implant characteristics and long-term lead electrical performance at 12 months

• Characterize the occurrence of complications related to the procedure or lead for His bundle pacing up to 12 months

Study Design	
This is a prospective, non-randomized, multi-site, clinical research study.
 
All subjects included in the study will be implanted with a Medtronic market released de novo Implantable Pacemaker, Medtronic SelectSecure™ MRI SureScan™ Model 3830 lead at the bundle of His for His bundle pacing, and compatible market released Medtronic Right Atrial lead (if applicable). The subjects with an implant of the Medtronic SelectSecure™ MRI SureScan™ Model 3830 lead for His bundle pacing will undergo a Cardiac CT Scan and be followed up to twelve months post implant for electrical testing. Subjects that do not receive an implanted SelectSecure™ MRI SureScan™ Model 3830 pacing lead for His bundle pacing will be exited from the study at the time of the unsuccessful implant or after any reportable Adverse Events are resolved.

Sample Size	
Up to 70 patients will be enrolled to ensure approximately 62 patients undergo an implant procedure.
 

• A sample size of 62 patients (who undergo an implant procedure) will produce a two-sided 95% confidence interval with a width equal to 0.15 for the implant success proportion when the observed implant success proportion is 0.9.

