### 13.2.5.3. Analysis Methods

The types of complications related to the procedure or the lead for His bundle pacing will be summarized using frequencies and percentages. The probability of a subject being free of a complication related to the procedure or the lead for His bundle pacing through 12 months post-implant will be estimated using the Kaplan-Meier method. In addition, the relationship between implant characteristics, including lead position, HB PCT at implant, and QRS duration at implant, and the occurrence of complications related to the procedure or the lead for His bundle pacing will be assessed using a Cox proportional hazard regression model.

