CRF	Case Report Form
HBP	His-Bundle Pacing
MUO	Medtronic Use Only
SAP	Statistical Analysis Plan

3. Introduction

The Imaging Study of Lead Implant for His Bundle Pacing (IMAGE-HBP) Study is a prospective, non-randomized, multi-site, clinical research study.

The purpose of this research study is to assess the implant success proportion of the Medtronic SelectSecure™ MRI SureScan™ Model 3830 pacing lead at the bundle of His for His bundle pacing, evaluate implant lead electrical measurements and changes over time, evaluate changes in QRS duration over time, estimate the correlation between lead location and selective vs. non-selective His-Bundle Pacing (HBP), and estimate the correlation between long-term lead performance and implant characteristics. Data from the study may be used to standardize the implant workflow to help improve the ease and predictability of His bundle pacing implants.

Up to 55 subjects will be enrolled from three sites to ensure 50 subjects undergo an implant procedure. Subjects will complete visits at enrollment/baseline, implant, pre-hospital discharge, 1 week, 3 months, 6 months and 12 months. The study duration is expected to be approximately 28 months from first center activation until closure.

This Statistical Analysis Plan (SAP) has been designed to document, before data is analyzed, the rationale for the study design, and the planned analyses related to the primary objective, secondary objectives and ancillary objectives. This SAP does not limit the analysis in reports, and additional analysis of the study data beyond this plan is expected.

The Imaging Study of Lead Implant for His Bundle Pacing study CIP Version 2.0, dated 29 Jun 2017 was used to create this SAP.

4. Study Objectives

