4.3. Ancillary Objectives

Additional analyses may be done on data and images collected during the study as outlined below. These analyses are descriptive in nature and are intended to provide additional information about His bundle pacing with the Medtronic SelectSecure™ MRI SureScan™ Model 3830 lead.

The ancillary objectives are:

1. To characterize performance of existing delivery tools and Medtronic SelectSecure™ MRI SureScan™ Model 3830 lead for HBP
2. To summarize implant procedure information
3. To characterize the survival for subjects up to 12 months post-implant.

5. Investigation Plan

The IMAGE-HBP Study is a prospective, non-randomized, multi-site, clinical research study.

All subjects included in the study will be implanted with a Medtronic market released de novo Implantable Pacemaker, Medtronic SelectSecure™ MRI SureScan™ Model 3830 lead at the bundle of His for His bundle pacing, and compatible market released Medtronic Right Atrial lead (if applicable). The subjects with an implant of the Medtronic SelectSecure™ MRI SureScan™ Model 3830 lead for His bundle pacing will undergo a Cardiac CT Scan and be followed up to twelve months post implant for electrical testing. Subjects that do not receive an implanted SelectSecure™ MRI SureScan™ Model 3830 pacing lead for His bundle pacing will be exited from the study at the time of the unsuccessful implant or after any reportable Adverse Events are resolved. Up to 55 subjects may be enrolled in the study.

The inclusion and exclusion criteria to be enrolled in the study are as follows:

Inclusion criteria

- Subject has a Class I or II indication for implantation of an implantable pacemaker according to ACC/AHA/HRS 2008 guidelines and any national guidelines¹⁵
- Subject (or legally authorized representative) has signed and dated the study-specific Consent Form
- Subject is 18 years of age or older, or is of legal age to give informed consent per local and national law
- Subject is expected to remain available for follow-up visits

Exclusion criteria

- Subject is contraindicated for Cardiac CT
- Subject has an existing or prior pacemaker, ICD or CRT device implant
- Subject is intended to receive an implant of a Left Ventricle lead or CRT device
- Subject life expectancy is less than 1 year
- Pregnant women or breastfeeding women, or women of child bearing potential and who are not on a reliable form of birth regulation method or abstinence

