7.4. Handling of Missing Data and Dropouts

If data is missing then there will be no imputation of the data. Instead, subjects with missing data will be excluded.

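### The complication Cox model in SAP 7.9.6 fits four parameters without a sparse-event method, so a lead-position hazard ratio could well be zero or infinite

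*SAP*

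**What the plan says.** Protocol 13.2.5.3 states that the relation of implant characteristics to procedure- or lead-related complications "will be assessed using a Cox proportional hazard regression model". SAP 7.9.6 repeats this and supplies PROC PHREG code with lead position as a class variable: "model monthsEvent*event(0) = leadloc pct0 pacedqrs0". SAP 7.9.2 gives lead position three levels (anterior, mid and posterior septum). The code has no penalty or exact option, and the text has no minimum event count, no rule for merging positions and no fallback.

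The two documents differ on size. SAP section 3, written from protocol version 2.0, has "Up to 55 subjects will be enrolled from three sites to ensure 50 subjects undergo an implant procedure". The current protocol synopsis has "Up to 70 patients will be enrolled to ensure approximately 62 patients undergo an implant procedure".

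Analysis Set #1 is assigned to this objective (SAP 7.1.3): "Study subjects will be included in this analysis set if an implant is attempted". Subjects who do not receive the study lead "will be exited from the study at the time of the unsuccessful implant or after any reportable Adverse Events are resolved" (SAP section 5). On missing data, SAP 7.4 says: "Instead, subjects with missing data will be excluded". For Secondary Objective #4, SAP 7.9.5 says of lead position: "The location determined from CT scan will be used in the analysis". SAP 7.9.6 does not state the source of lead position.

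**The concern.** A complication is a narrow event here. Under protocol Table 4 it must be fatal, end significant device function or need an invasive intervention, and this objective counts only those related to the procedure or the lead. Few events are therefore plausible. In an unpenalised Cox model, a position with no events has no finite maximum-likelihood coefficient. Its hazard ratio against the reference runs to zero, and if the empty position is itself the reference, the other contrasts run to infinity. The software may still print a number with a huge standard error.

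What is at stake is the set of hazard ratios linking implant characteristics to complications. They could be non-finite, or have very wide limits, without any count by position to explain why. A method chosen after the events are seen would no longer be pre-specified.

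**Working it through.** **The plan's own precision figures.** These concern the primary endpoint only. The Wilson width is 2z·√(p(1−p)/n + z²/4n²) / (1 + z²/n), with z = 1.96. For 56/62 it is 0.1504 (protocol: 0.15), and for 45/50 it is 0.1701 (SAP: 0.17). Both reproduce. No event count or precision is given for the Cox model, so there is no plan figure to reproduce there.

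**Inputs.**
- Parameters: two for lead position, one for implant HB PCT and one for paced QRS, making 4 (SAP 7.9.6).
- Attempts N: 50 (SAP) or 62 (protocol).
- Complication rate r by 12 months: not given; assumed 5, 10 and 15%.
- Position shares p: not given; assumed equal thirds, then 60/30/10.

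**Expected events, N × r, and events per parameter, N × r / 4.**
- N = 50: 2.5, 5.0 and 7.5 events, or 0.6, 1.25 and 1.9 per parameter.
- N = 62: 3.1, 6.2 and 9.3 events, or 0.8, 1.55 and 2.3 per parameter.

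**Chance of at least one position without events.** This assumes no true position effect and counts zero events overall as empty. By inclusion-exclusion,

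P = Σ(1 − r·pⱼ)^N − Σ(1 − r(pⱼ + pₖ))^N + (1 − r)^N.

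For equal thirds this is 3(1 − r/3)^N − 3(1 − 2r/3)^N + (1 − r)^N. At N = 62 and r = 0.10 it is 3 × 0.1222 − 3 × 0.0139 + 0.0015 = 0.326.

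| N | Shares | r = 5% | r = 10% | r = 15% |
|---|---|---|---|---|
| 50 | equal | 82% | 46% | 22% |
| 62 | equal | 73% | 33% | 12% |
| 50 | 60/30/10 | 91% | 71% | 53% |
| 62 | 60/30/10 | 86% | 62% | 43% |

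**Effect of exclusions.** Suppose 10% of attempts leave no lead in place and so have no position. The 10% comes from the plan's 0.9 success scenario and assumes that every failure has no lead. The fit then has 50 × 0.9 = 45 or 62 × 0.9 ≈ 56 subjects. The equal-thirds chances become 86, 53 and 27% at 45, and 78, 39 and 16% at 56.

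**By event count.** With k events and equal positions the chance is 3(2/3)^k − 3(1/3)^k. For k = 3, 6, 9 and 12 this is 78, 26, 8 and 2%. With one or two events, at least one of three positions must be empty. At N = 62 the binomial chance of exactly one or two events is 56% at a 3% rate and 35% at 5%.

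**Simulated Cox fits.** The set-up was N = 62, equal positions, standard normal PCT and QRS, no true association, and non-events followed to 12 months. The non-finite share was 79, 25, 8 and 2% at 3, 6, 9 and 12 events, in line with the exact values. Among finite fits, the median ratio of upper to lower 95% limit for a position hazard ratio was about 94, 33 and 20 at 6, 9 and 12 events.

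**Firth fits in the same setting.**
- Estimates were finite in 99.9% of data sets at 3 events and in all at 6, 9 and 12.
- The share with a position contrast above 3, below 1/3 or non-finite fell from 78 to 61% (3 events), 55 to 42% (6; 39% in a second run), 41 to 31% (9) and 30 to 22% (12).
- Median profile-limit ratios were about 81, 27 and 21 at 6, 9 and 12 events, from only 60 data sets each.

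**The case against.** The strongest reply is that the analysis is descriptive with no performance requirement (SAP 4.2), the code is only indicative, and SAP section 3 expects further analyses, so Firth's method is not ruled out. Wide limits are also an honest picture of few events. All of that stands, and it caps the severity. But permission to repair is not a planned repair. The SAP's one data-sufficiency rule (7.9.1, about 10 patients) covers primary-endpoint subgroups only.

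Four stronger readings are tempting, and the documents do not support them.
- A reader might infer that no event counts will appear. SAP 7.9.6 already plans complication frequencies, a table by MedDRA term and a listing of every event. Only counts by position and within the fitted subset are missing.
- A reader might infer that exclusions are ignored. SAP 7.1.1 says that subjects whose missing data prevent an analysis leave that objective, and 7.1.3 promises a flow diagram of exclusions. That diagram is framed around the primary objective, so cover for the Cox subset is partial, not absent.
- A reader might take 70 as the number of attempts. It is the protocol's enrolment cap.
- A reader might conclude that the fit reduces exactly to Analysis Set #2, or that it clearly does not. The documents do not settle whether a failed attempt with the lead left in place goes on to CT, and 7.9.6 does not say that position is CT-derived.

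It can also be said that Firth's method gains little. It does little for precision, and finite ratios from one or two events could look more credible than a visible failure to estimate. That objection is sound and shapes the fix.

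**Conclusion.** The point holds and is minor. SAP 7.9.6 pre-specifies an unpenalised four-parameter Cox fit in 50 or approximately 62 attempts, less exclusions, with no provision for few events. At assumed rates of 5 to 15% and equal positions, the chance of a zero or infinite position hazard ratio is 82 to 22% at 50 attempts and 73 to 12% at 62. It is higher with unequal positions.

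The size rests on the assumed rate and position split. Failure is not certain: near 12 events with balanced positions it is rare (2%), and the remaining weakness is imprecision. Only these hazard ratios are affected. It would go too far to say that the complication results as a whole are unreliable, since the frequencies, the Kaplan-Meier estimates and the primary endpoint do not depend on this model.

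**What to change.** In SAP 7.9.6:
1. Keep the model, but fit it with Firth's penalised likelihood and profile-likelihood limits (PHREG MODEL options `FIRTH` and `RISKLIMITS=PL`).
2. Beside the hazard ratios, show the number of subjects and events actually in the fit, overall and by lead position.
3. If there are no complications, or only one or two, report counts by position without hazard ratios.

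Two editorial changes belong with this: replace the undefined data set name `analysisset` with the intended one, and cross-refer to the CT-derived position if that is what is meant.

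The cost is two SAS options, one small table and a few sentences. The downside is slight shrinkage of the estimates. Because Firth's method leaves the limits wide, item 2 is needed as much as item 1.
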